5.3 Baseline Visit (prior to dosing)

Subjects who meet all eligibility criteria and have signed informed consent will be discussed with the CCC for authorization to randomize. After the CCC verifies eligibility of the subject

and authorizes randomization, the subject will be randomized by the site via an automated phone/internet system.

Once the subject is randomized, the automated system will provide the study staff with a unique randomization number for the subject and an assigned investigational product kit number. The assigned kit should be ordered or obtained by the PI or designee from the pharmacy or applicable investigational product storage location.

For each study subject the following data/assessments are required to be collected:

The following data/assessments may have preceded the time of the last inclusion criteria and consent as the information is collected as part of the medical record. However, no data is collected until the subject has been consented.

- Demographics, height and weight (actual baseline dry weight since hospital admission or if unavailable, usual body weight. If weight is unavailable, estimated body weight can be used).
- Medical history (all known information regarding the subject's health history/relevant surgeries/interventions).
- Acute Physiology and Chronic Health Evaluation (APACHE) II^{29,30} (timeframe for data collection is the 24 hours prior to the first dose, See [Appendix K](#) and [Appendix L](#))
- Concomitant medications administered within the 7 days prior to randomization (including fluids for resuscitation and blood products).
- Historical information regarding treatment for the current episode of sepsis.
- Documentation of the infection (site of infection and, if available: positive culture results, prior antibiotics, sensitivity of cultured organism to antibiotics, nonmedical treatment such as surgery or drainage)
- Assessment of ICU stay and hospitalization
- Complete the Organ Dysfunction (OD) assessments of Shock, Ventilator, Dialysis
- If Respiratory dysfunction: duration on mechanical ventilation, qualifying PaO₂/FiO₂ ratio prior to randomization.
- If Cardiovascular Dysfunction: fluid administration, CVP, and/or PAWP, duration on vasopressors, name of vasopressor currently administered.
- If the subject is receiving dopamine, dobutamine, or other inotropes for cardiac dysfunction, record the dose.
- Record Interventions/Surgeries

The following assessments are to be performed/collected after the consent has been obtained, last inclusion criteria is met, and authorization to randomize has been received from the CCC:

- Vital signs: Pulse – beats per minute (BPM), Blood Pressure (BP) mmHg, Respirations – breaths per minute, Temperature
- Changes in concomitant medications
- Blood Product administration
- Physical Examination including the following: general appearance, Head, Eye, Ear Nose Throat (HEENT), neck, respiratory, cardiovascular, chest, abdomen, lymphatic, musculoskeletal and extremities, skin and neurologic examination
- 12 lead ECG: to be read centrally
- Adverse Events/Serious Adverse Events
- Assessment of ICU stay and hospitalization
- Complete the Organ Dysfunction (OD) assessments of Shock, Ventilator, Dialysis
- Interventions/Surgeries
- Major Bleeding Events

Blood will be obtained for following local laboratory tests:

- Serum Chemistry (Creatinine and Total bilirubin)
- PaO₂/FiO₂ (only for respiratory dysfunction)
- Complete Blood Count with differential (RBC, Hemoglobin, Hematocrit, and WBC with differential count)
- Platelet count
- Coagulation Panel (Prothrombin time and INR)

Additional labs will be drawn for analysis at the central laboratory:

- Serum Chemistry (Na, K, Cl, Bicarbonate, Glucose, Ca, BUN, Creatinine, ALT, AST, Alkaline Phosphatase and Total bilirubin)
- D-dimer
- Plasma thrombomodulin concentration (PK)
- Exploratory Laboratory Tests
 - Coagulation: functional protein C, TAT, F1.2, PAI-1 and ATIII

- Inflammation: CRP, Microparticles, and C5a
 - Arterial lactate concentration
 - Anti-drug Antibodies to ART-123

For randomized subjects who do not receive any study drug all study tests completed prior to the point it was known the subject would not be dosed will be collected. All AEs, SAEs and survival status through Day 28 will be collected, but further study visits/procedures (including ETT) will not be performed.

5.4 Dosing Visit (Day 1)

The first dose of study drug must be administered as soon as possible and within 4 hours after randomization. For post-surgical subjects see Section 2.6.3. Follow the instructions in the Drug Accountability and Handling Manual for proper preparation and administration instructions.

Within one hour after the administration of the first dose record the following:

- Vital signs
- Changes in concomitant medications
- Blood Product administration
- Adverse Events/Serious Adverse Events
- Assessment of ICU stay and hospitalization
- Complete the Organ Dysfunction (OD) assessments of Shock, Ventilator, Dialysis
- PaO₂/FiO₂ if available within one hour after IP administration (only if vented)
- Interventions or Surgeries
- Major Bleeding Events
- Assessment of the degree of burden and risk threshold, and assess continuation of treatment with ART-123/placebo (refer to **Section 7.5**)

5.5 Day 2 Visit

On Day 2, administration of the second dose of study medication will begin 24 hours (± 2 hours) after the first dose was given (dosing Day 1). Please refer to **Section 3** if the subject has had an intervention/procedure since the first dose of study drug.

Within one (1) hour after study drug administration, perform/record the following:

- Vital signs
- Changes in concomitant medications
- Blood product administration
- Adverse Events/Serious Adverse Events
- Assessment of ICU stay and hospitalization
- Complete the Organ Dysfunction (OD) assessments of Shock, Ventilator, Dialysis
- Interventions/Surgeries
- Major Bleeding Events
- Assessment of the degree of burden and risk threshold, and assess continuation of treatment with ART-123/placebo (refer to **Section 7.5**)

Blood will be obtained for following local laboratory tests:

- PaO₂/FiO₂ (only if vented and not collected as SOC)
- Complete Blood Count with differential (RBC, Hemoglobin, Hematocrit, and WBC with differential count)
- Platelet count
- Coagulation Panel: Prothrombin time and INR

Additional blood samples will be drawn for analysis at the central lab:

- Serum Chemistry (Na, K, Cl, Bicarbonate, Glucose, Ca, BUN, Creatinine, ALT, AST, Alkaline Phosphatase and Total bilirubin)
- D-dimer

5.6 Day 3 Visit (Pre-dose)

On Day 3, administration of the third dose of study medication will begin 48 hours (± 2 hours) after the first dose of study medication was given (Dosing Day 1). Please refer to **Section 3** if the subject has had an intervention/procedure since the first dose of study drug.

Within one (1) hour PRIOR to study drug administration, blood samples will be collected for the following central laboratory tests:

- Plasma thrombomodulin concentration (PK)

- Exploratory Laboratory Tests
 - Coagulation: functional protein C, TAT, F1.2, PAI-1 and ATIII
 - Inflammation: CRP, Microparticles, and C5a

5.7 Day 3 Visit (Post-dose)

Within one (1) hour after study drug administration, perform/record the following:

- Vital signs
- Changes in concomitant medications
- Blood product administration
- 12 lead ECG: to be read centrally
- Adverse Events/Serious Adverse Events
- Assessment of ICU stay and hospitalization
- Complete the Organ Dysfunction (OD) assessments of Shock, Ventilator, Dialysis
- Interventions/Surgeries
- Major Bleeding Events
- Assessment of the degree of burden and risk threshold, and assess continuation of treatment with ART-123/placebo (refer to **Section 7.5**)

Blood will be obtained for following local laboratory tests:

- PaO₂/FiO₂ (only if vented and not collected as SOC)
- Complete Blood Count with differential (RBC, Hemoglobin, Hematocrit, and WBC with differential count)
- Platelet count
- Coagulation Panel (Prothrombin time and INR)

Additional labs will be drawn for analysis at the central lab:

- Serum Chemistry (Na, K, Cl, Bicarbonate, Glucose, Ca, BUN, Creatinine, ALT, AST, Alkaline Phosphatase and Total bilirubin)
- D-dimer
- Plasma thrombomodulin concentration (PK)

- Exploratory Laboratory Tests
 - Coagulation: functional protein C, TAT, F1.2, PAI-1 and ATIII
 - Inflammation: CRP, Microparticles, and C5a

5.8 Days 4-6 Visits

On Days 4, 5 and 6 administration of the fourth, fifth and sixth doses of study medication will begin 72, 96 and 120 hours (± 2 hours) after the first dose of study drug was administered, respectively. Please refer to **Section 3** if the subject has had an intervention/procedure since the first dose of study drug.

Within one (1) hour after the administration of study drug (doses 4-6), perform/record the following:

- Vital Signs
- Changes in concomitant medications
- Blood product administration
- Adverse Events/Serious Adverse Events
- Assessment of ICU stay and hospitalization
- Complete the Organ Dysfunction (OD) assessments of Shock, Ventilator, Dialysis
- Interventions/Surgeries
- Major Bleeding Events
- Assessment of the degree of burden and risk threshold, and assess continuation of treatment with ART-123/placebo (refer to **Section 7.5**)

Blood will be obtained for the following local laboratory tests on Days 4 and 6 only:

- PaO₂/FiO₂ (only if vented and not collected as SOC)
- Complete Blood Count with differential (RBC, Hemoglobin, Hematocrit, and WBC with differential count)
- Platelet count
- Coagulation Panel (Prothrombin time and INR)

Additional labs on Days 4 and 6 only will be drawn for analysis at the central laboratory:

-
- Serum Chemistry (Na, K, Cl, Bicarbonate, Glucose, Ca, BUN, Creatinine, ALT, AST, Alkaline Phosphatase and Total bilirubin)
 - D-dimer

On study Day 5 only, blood will be obtained for the following local laboratory test:

- PaO₂/FiO₂ (only if vented and not collected as SOC)

On study Day 6 only, the following will be performed:

- 12 lead ECG: to be read centrally
- Blood will be drawn for analysis at the central laboratory:
 - Plasma thrombomodulin concentration (PK)
 - Exploratory Laboratory Tests
 - Coagulation: functional protein C, TAT, F1.2, PAI-1 and ATIII
 - Inflammation: CRP, Microparticles, and C5a

Days 4-6

If the QTcB is >500 msec or the QTcB is > 60 msec over the baseline value, continue to monitor ECGs once daily until the earlier of Day 14 or the time when such conditions are no longer met. In the event of hospital discharge at this time, the Investigator should carefully evaluate these parameters prior to hospital discharge.

5.9 Day 7 Visit

On Day 7, assessments will begin 144 hours (\pm 2 hours) after the first dose (dosing Day 1) of study drug was administered. If a subject is discharged on Day 7, the Day 7 Visit, not the Hospital Discharge Visit, is performed.

Perform/record the following:

- Vital Signs
- Changes in concomitant medications
- Blood product administration
- 12 lead ECG: to be read centrally
- Adverse Events/Serious Adverse Events
- Assessment of ICU stay and hospitalization

-
- Complete the Organ Dysfunction (OD) assessments of Shock, Ventilator, Dialysis
 - Interventions/Surgeries
 - Major Bleeding Events

Blood will be obtained for following local laboratory tests:

- PaO₂/FiO₂ (only if vented and not collected as SOC)
- Complete Blood Count with differential (RBC, Hemoglobin, Hematocrit, and WBC with differential count)
- Platelet count
- Coagulation Panel (Prothrombin time and INR)

Additional blood samples will be drawn for analysis at the central laboratory:

- Serum Chemistry (Na, K, Cl, Bicarbonate, Glucose, Ca, BUN, Creatinine, ALT, AST, Alkaline Phosphatase and Total bilirubin)
- D-dimer
- Plasma thrombomodulin concentration (PK)
- Exploratory Laboratory Tests
 - Coagulation: functional protein C, TAT, F1.2, PAI-1 and ATIII
 - Inflammation: CRP, Microparticles, and C5a
- Arterial lactate concentration

If the QTcB is >500 msec or the QTcB is > 60 msec over the baseline value, continue to monitor ECGs once daily until the earlier of Day 14 or the time when such conditions are no longer met. In the event of hospital discharge at this time, the Investigator should carefully evaluate these parameters prior to hospital discharge.

5.10 Early Treatment Termination (ETT) Visit

The ETT visit is for subjects who discontinue study drug treatment early and remain hospitalized or who are discharged from the hospital on Study Days 1-6. The ETT Visit assessments are to be done in place of the daily assessments required for the actual study visit day.

-
- For subjects who discontinue treatment early (prior to the 6th dose) and remain hospitalized: the ETT is performed 24 hours (± 2 hours) after the last dose of study medication that was administered.
 - For subjects discharged from the hospital on Study Days 1-6: the ETT is performed (not the Hospital Discharge Visit),

Note: Any subject who completes the ETT visit remains in the study. If the subject is still hospitalized, study visits must continue to be completed. All subjects discharged from the hospital before Day 14 must return for Day 14 and Day 28 visit procedures. Subjects discharged from the hospital after Day 14 but before Day 28 must return for Day 28 procedures. All subjects must be contacted at 3, 6 and 12 months for survival status.

Record the following:

- Vital Signs
- Changes in concomitant medications
- Blood product administration
- 12 lead ECG: to be read centrally
- Adverse Events/Serious Adverse Events
- Assessment of ICU stay and hospitalization
- Complete the Organ Dysfunction (OD) assessments of Shock, Ventilator, Dialysis
- Interventions/Surgeries
- Major Bleeding Events

Blood samples will be obtained for following local laboratory tests:

- PaO₂/FiO₂ (only if vented and not collected as SOC)
- Complete Blood Count with differential (RBC, Hemoglobin, Hematocrit, and WBC with differential count)
- Platelet count
- Coagulation Panel (Prothrombin time and INR)

Additional blood samples will be drawn for analysis at the central lab:

- Serum Chemistry (Na, K, Cl, Bicarbonate, Glucose, Ca, BUN, Creatinine, ALT, AST, Alkaline Phosphatase and Total bilirubin)

- D-dimer
- Plasma thrombomodulin concentration (PK)
- Exploratory Laboratory Tests
 - Coagulation: functional protein C, TAT, F1.2, PAI-1 and ATIII
 - Inflammation: CRP, Microparticles, and C5a
- Arterial lactate concentration

If the QTcB is >500 msec or the QTcB is > 60 msec over the baseline value, continue to monitor ECGs once daily until the earlier of Day 14 or the time when such conditions are no longer met. In the event of hospital discharge at this time, the Investigator should carefully evaluate these parameters prior to hospital discharge.

5.11 Days 8-13

Beginning with Day 8 all prospective visits are based on calendar days. From this visit forward days are calendar days and are counted as follows: first dose on Day 1=1, D2=2, etc.

On study days 8-13, the following assessments will be completed as long as the subject remains in the hospital:

Perform/record the following:

- Changes in concomitant medications
- Blood product administration
- Adverse Events/Serious Adverse Events
- Assessment of ICU stay and hospitalization
- Complete the Organ Dysfunction (OD) assessments of Shock, Ventilator, Dialysis and if the subject is vented, collect blood for PaO₂/FiO₂ (if not done as SOC)
- Interventions/Surgeries
- Major Bleeding Events

If the QTcB is >500 msec or the QTcB is > 60 msec over the baseline value, continue to monitor ECGs once daily until the earlier of Day 14 or the time when such conditions are no longer met. In the event of hospital discharge at this time, the Investigator should carefully evaluate these parameters prior to hospital discharge.

5.12 Day 14 (+ 3 days)

Subjects must return to the hospital for Day 14 procedures (+3 day deviation is acceptable). For subjects who remain hospitalized, this visit's procedures are performed on Day 14. If a subject is to be discharged on Day 13, the Day 14 Visit procedures must be performed in lieu of the procedures scheduled for Day 13. Subjects who are discharged from the hospital on the same day as the Day 14 Visit, complete the Day 14 Visit not the Hospital Discharge Visit.

Perform/record the following:

- Vital signs
- Changes in concomitant medications
- Blood product administration
- 12 lead ECG: to be read centrally
- Adverse Events/Serious Adverse Events
- Assessment of ICU stay and hospitalization
- Complete the Organ Dysfunction (OD) assessments of Shock, Ventilator, Dialysis
- Interventions/Surgeries
- Major Bleeding Events

Blood will be obtained for following local laboratory tests:

- PaO₂/FiO₂ (only if vented and not collected as SOC)
- Complete Blood Count with differential (RBC, Hemoglobin, Hematocrit, and WBC with differential count)
- Platelet count
- Coagulation Panel (Prothrombin time and INR)

Additional blood samples will be drawn for analysis at the central laboratory:

- Serum Chemistry (Na, K, Cl, Bicarbonate, Glucose, Ca, BUN, Creatinine, ALT, AST, Alkaline Phosphatase and Total bilirubin)
- D-dimer
- Plasma thrombomodulin concentration (PK)
- Exploratory Laboratory Tests
 - Coagulation: functional protein C, TAT, F1.2, PAI-1 and ATIII

- Inflammation: CRP, Microparticles, and C5a
- Anti-drug antibodies to ART-123

5.13 Days 15-27

On study days 15-27, the following assessments will be completed as long as the subject remains in the hospital:

Perform/record the following:

- Changes in concomitant medications
- Blood product administration
- Adverse Events/Serious Adverse Events
- Assessment of ICU stay and hospitalization
- Complete the Organ Dysfunction (OD) assessments of Shock, Ventilator, Dialysis and if the subject is vented, collect blood for PaO₂/FiO₂ (if not done as SOC)
- Interventions/Surgeries
- Major Bleeding Events

5.14 Hospital Discharge

This visit applies to subjects discharged from the hospital on Day 8 up to Day 28 except for Days 13 / 14 or Day 28 in which case please refer to the respective study visit for study procedures.

Perform/record the following prior to discharge:

- Vital signs
- Changes in concomitant medications
- Blood product administration
- 12 lead ECG: to be read centrally

Note: If the QTcB is >500 msec or the QTcB is > 60 msec over the baseline value, continue to monitor ECGs once daily until the earlier of Day 14 or the time when such conditions are no longer met. In the event of hospital discharge at this time, the

Investigator should carefully evaluate these parameters prior to hospital discharge. Upon meeting this condition, the Hospital Discharge Visit is to be performed.

- Adverse Events/Serious Adverse Events
- Assessment of ICU stay and hospitalization
- Complete the Organ Dysfunction (OD) assessments of Shock, Ventilator, Dialysis
- Interventions/Surgeries
- Major Bleeding Events

Blood will be obtained for following local laboratory tests:

- PaO₂/FiO₂ (only if vented and not collected as SOC)
- Complete Blood Count with differential (RBC, Hemoglobin, Hematocrit, and WBC with differential count)
- Platelet count
- Coagulation Panel (Prothrombin time and INR)

Additional labs will be drawn for analysis at the central lab:

- Serum Chemistry (Na, K, Cl, Bicarbonate, Glucose, Ca, BUN, Creatinine, ALT, AST, Alkaline Phosphatase, and Total bilirubin)
- D-dimer
- Plasma thrombomodulin concentration (PK)
- Exploratory Laboratory Tests
 - Coagulation: functional protein C, TAT, F1.2, PAI-1 and ATIII
 - Inflammation: CRP, Microparticles, and C5a
- Anti-drug antibodies to ART-123

All subjects discharged from the hospital before Day 14 must return for Day 14 and Day 28 visit procedures. Subjects discharged from the hospital after Day 14 but before Day 28 must return for Day 28 procedures.

All subjects must be contacted at 3, 6 and 12 months for survival status.

5.15 Day 28 (+3 days) or End of Study Visit

For subjects who remain hospitalized, assessments will be performed on the 28th day using the first dosing day as Day 1. Subjects who were discharged must return to the hospital for this visit so safety assessments can be performed. For subjects who were discharged from the hospital prior to Day 28, there is a visit window of +3 days and the subject must return on Day 28–31 for the completion of this visit. If a subject is unable or unwilling to return to the hospital for this visit, it may be conducted via telephone and any required assessments that cannot be done will be recorded as protocol deviations (i.e., laboratory draws). Telephone based assessments will document the date of the call, the name of the person initiating the call, the name and relationship to the subject of the person providing the information if the subject is unable to do so, and the survival status of the subject. Additionally, the subject/person providing the information will be asked about any potential adverse events, significant bleeding inclusive of any major bleeding events, or re-hospitalizations that the subject may have had since their discharge date and any changes to medications they are taking.

The End of Study Visit occurs whenever the subject discontinues study participation (as defined in **Section 2.7.2.2**) from the **study** prior to Day 28.

Perform/record the following:

- Changes in concomitant medications
- Blood product administration
- Adverse Events/Serious Adverse Events
- Assessment of ICU stay and hospitalization
- Complete the Organ Dysfunction (OD) assessments of Shock, Ventilator, Dialysis
- Interventions/Surgeries
- Major Bleeding Events

Blood will be obtained for following local laboratory tests:

- PaO₂/FiO₂ (only if vented and not collected as SOC)
- Complete Blood Count with differential (RBC, Hemoglobin, Hematocrit, and WBC with differential count)
- Platelet count
- Coagulation Panel (Prothrombin time and INR)

Additional blood samples will be drawn for analysis at the central laboratory:

- Serum Chemistry (Na, K, Cl, Bicarbonate, Glucose, Ca, BUN, Creatinine, ALT, AST, Alkaline Phosphatase and Total bilirubin)
- Anti-drug antibodies to ART-123. Additionally, all subjects that develop anti-drug antibodies to ART-123 will be followed for blood draw and medical evaluation at 3 months intervals until their serum antibody titer results become negative for a maximum duration of 18 months. Serum samples from subjects that have demonstrated the development of antidrug antibodies that are present on Day 28 or End of Study Visit will be tested for the presence of neutralizing antibodies.

Note: Survival status for all subjects must be reflective of survival status on calendar Day 29.

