5.18 Follow-Up Visits for Subjects who have an anti-ART-123 antibody

Any subject with positive anti-ART-123 antibody results will return to the site at 3 month intervals for collection of a blood sample to be used for determination of presence or absence

of the antibody. Serum samples from subjects that have demonstrated the development of antidrug antibodies that are present on Day 28 or at the “End of Study” Visit will be tested for the presence of neutralizing antibodies.

This process will be continued every 3 months until antibody results are negative or until the subject’s 18 month Follow-Up Visit. Sites will be informed when subjects are antibody positive.

SAEs/thrombotic events information in these antibody positive subjects will be collected and reported to the sponsor over a maximum of 18 months or subject becoming antibody negative, whichever is earlier.

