Interventions / Surgeries		X	X	X		X	X	X	X	X	X	X	X	X	X	X			
Major Bleeding Events		X	X	X		X	X	X	X	X	X	X	X	X	X	X			
Assessment of the degree of burden and risk threshold, and assess continuation of treatment with ART-123/placebo			X	X		X	X	X	X										
Dispense ART-123/Placebo ²			X	X		X	X	X	X										
Survival Status															X	X	X	X	

Table Footnotes:

- a EOS = End of Study – When a subject is discontinued from the study prior to Day 28 for any reason other than Death (i.e., withdrawal of consent as defined in **Section 2.7.2**). This does not include the subjects who discontinue study drug early, but remain in the study for all other assessments.
- b This visit is performed when a subject is discharged from the hospital on Study Days 1-6 or when a subject remains hospitalized and discontinues study drug administration prior to the 6th dose. The Early Treatment Termination Visit is performed 24 hours (± 2 hours) after the last dose of study medication if study drug administration was discontinued early or this window does not apply. This visit is done in place of the daily study visit.
 1. If the subject is to be discharged from the hospital on Day 13 perform the Day 14 visit in place of Day 13 visit (Hospital Discharge visit is not performed). ONLY if subject has been discharged from the hospital is there a +3 day window for the subject to return for the Day 14 assessments and labs. Subjects who remain hospitalized for Day 14 must have the assessments performed on the 14th calendar day.
 2. **The first dose of study drug must be administered as soon as possible after randomization and within 4 hours. For post-surgical patients that had potentially hemorrhagic surgery the first dose of study drug must not be administered within 12 hours of major surgery.** (See Section 2.6.3.) **All dosing times are based on the first dose of drug. The windows are: Day 2: 24 hours (± 2 hours), Day 3: 48 hours (± 2 hours), Day 4: 72 (± 2 hours), Day 5: 96 hours (± 2 hours) and Day 6: 120 hours (± 2 hours). If IP is held due to surgery refer to Section 3.** Dosing is discontinued when a subject is discharged from the hospital. Administration of study drug is contraindicated if the co-administration of excluded concomitant medication (e.g. full heparinization, oral anticoagulant, anti-platelets drug) is required for subject treatment, or has an intolerable adverse event, such as bleeding events or conditions that place the subject at high risk of bleeding.

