7.6.3 Laboratory Sample Categories

There are four types of clinical laboratory evaluations: Safety, Coagulation Panel, Organ Dysfunction, and Exploratory.

Safety laboratory tests include the following:

- Serum Chemistry: Chemistry (Na, K, Cl, Bicarbonate, Glucose, Ca, BUN, Creatinine, ALT, AST, Alkaline Phosphatase, Total bilirubin)
- Complete Blood Count with differential (RBC, Hemoglobin, Hematocrit, and WBC with differential count)
- Pregnancy test: Serum or Urine hCG
- Platelet count
- Antibodies to ART-123.

Note: All subjects that develop positive antibodies to ART-123 at Day 28 will be followed at 3 month intervals until their serum antibody titer level returns back to baseline or for a maximum of 18 months.

Coagulation Panel includes the following tests:

- Prothrombin time

- INR
- D-dimer

Organ Dysfunction labs include the following tests:

- Serum creatinine
- Total bilirubin
- PaO₂/FiO₂ ratio

Exploratory labs include the following tests:

- Coagulation: functional protein C, TAT, F1.2, PAI-1 and ATIII
- Inflammation: CRP, Microparticles, and C5a
- Plasma thrombomodulin concentration (PK)
- Arterial lactate concentration

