#### 4.4.3 Antibody Analysis (Anti-drug antibody to ART-123)

Anti-drug antibodies to ART-123 will be evaluated and presented in a listing. A summary of antibody analysis results will be presented by treatment group, overall, and for each visit. This summary table will include the number of screening assays analyzed and the number and percent of subjects having positive and negative results from the analyzed assay including the screening and confirmatory assay. All collected antibody data will be presented in a by subject listing. Titer and Neutralizing antibody results will only be available for subjects with confirmed positive ADA results.

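### Neutralizing-antibody testing is tied to anti-drug antibodies present on Day 28 or at End of Study, leaving no stated route to a result for an earlier positive who dies or turns negative first

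*Protocol*

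**What the plan says.** Anti-drug antibody samples are drawn at baseline (Protocol 5.3), Day 14 (5.12), hospital discharge from Day 8 onward (5.14) and Day 28 or End of Study (5.15).

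The neutralizing assay has one stated trigger. Protocol 5.15 says that samples from subjects with "antidrug antibodies that are present on Day 28 or End of Study Visit will be tested for the presence of neutralizing antibodies", and 5.18 repeats the condition ("Visit will be tested for the presence of neutralizing antibodies").

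End of Study is narrow. Section 5.15 says "The End of Study Visit occurs whenever the subject discontinues study participation" and points to 2.7.2.2, which covers withdrawal of consent. Death is handled separately in 2.7.2.1. Table 1 footnote a (Protocol 5.19) gives the same limit: "When a subject is discontinued from the study prior to Day 28 for any reason other than Death".

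Two other places mention the assay without a visit. Protocol 4.1 lists neutralizing antibodies beside anti-drug antibodies as a central laboratory test. SAP 4.4.3 says "Titer and Neutralizing antibody results will only be available for subjects with confirmed positive ADA results".

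**The concern.** Under the trigger as written, whether a subject gets a neutralizing result depends on what happens after the positive sample is taken. The subject must survive to Day 28 and still be positive then. Among subjects with a confirmed positive on Day 14 or at discharge, those tested are therefore a selected group, and transient positives and later deaths drop out.

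The protocol follows antibody-positive subjects for serious adverse events and thrombotic events for up to 18 months (5.18, 7.2), so it treats a positive finding as worth characterizing. If a Day 14 positive has a fatal event on, say, Day 20, the serum has been drawn but no passage sends it for the neutralizing assay. A reader of the study report could not tell whether a missing result meant not neutralizing, not tested or not eligible for testing, unless the rule is spelled out.

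**Working it through.** No stated figure in the plan bears on this point, so the main check is a comparison of passages. The arithmetic only gives scale.

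**Tracing a subject confirmed positive on Day 14 or at discharge**

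- *Alive, attends and still positive on Day 28:* meets the trigger in 5.15 and 5.18. A neutralizing result is expected.
- *Withdraws consent before Day 28:* has an End of Study visit, and is tested if a sample is drawn there and is positive.
- *Dies before Day 28:* has no Day 28 visit, and End of Study does not apply (Table 1 footnote a; 5.15 with 2.7.2.2). No route is stated.
- *Negative on Day 28:* antibodies are not present at the qualifying visit. No route is stated.
- *Day 28 done by telephone (allowed in 5.15, with missed draws recorded as deviations):* no Day 28 sample exists, but 5.18 recalls any antibody-positive subject every 3 months ("This process will be continued every 3 months until antibody results are negative"). Whether the neutralizing assay is run on those later samples is not clear. The note in 7.6.3 words the recall more narrowly ("All subjects that develop positive antibodies to ART-123 at Day 28 will be followed").

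SAP 4.4.3 makes a confirmed positive a necessary condition for a neutralizing result. It does not say that every confirmed positive is tested, so it does not extend the protocol's trigger. Protocol 4.1 gives no timing and does not extend it either.

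**Scale in the ART-123 arm**

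Inputs from Protocol 10.1: 16% assumed 28-day mortality, and 800 subjects randomized 1:1, so 400 per arm. The documents do not give the timing of deaths. I assume that a share *e* of the deaths, 60% to 75%, falls before Day 14.

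P(die between Day 14 and Day 28, given alive at Day 14) = 0.16 × (1 − *e*) / (1 − 0.16 × *e*)

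- *e* = 0.75: 0.04 / 0.88 = 4.5%, or 400 × 0.04 = 16 subjects
- *e* = 0.60: 0.064 / 0.904 = 7.1%, or 400 × 0.064 ≈ 26 subjects

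Only the antibody-positive ones among these 16 to 26 are affected. No antibody rate is given. If it were 1% to 10% (an assumption), the count would be 16 × 0.01 ≈ 0.2 to 25.6 × 0.10 ≈ 2.6 subjects.

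A wider assumption, that 10% to 50% of the 400 × 0.16 = 64 ART-123 deaths follow an earlier antibody sample, gives about 6 to 32 subjects before applying any antibody rate. The number who turn negative by Day 28 cannot be computed from the documents.

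**The case against.** The strongest reply is that the trigger says which subjects will be tested and forbids nothing else. Protocol 4.1 and SAP 4.4.3 carry no Day 28 limit and leave room for testing any confirmed positive. This stands in part. A reader might infer that the affected subjects are never tested, but the documents support only that no route to testing is stated for them.

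A reader might also infer that a secondary endpoint is compromised. It is not. The secondary objective and the secondary safety endpoint concern anti-drug antibodies, and neither names neutralizing status. A Day 14 positive who later dies still counts, because SAP 4.4.3 summarizes antibody results by visit. The summary table it describes covers screening and confirmatory results and no neutralizing results.

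A third inference is that the neutralizing result matters most in those who die. The documents do not support this. Protocol 2.3 gives a half-life of about 20 hours and puts ten half-lives at 8 days after the last dose, which is about Day 14 after six days of dosing. Little study drug would then remain to be neutralized. Serious adverse events through Day 28 are collected whatever the antibody status.

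Telephone visits should not be counted as permanent losses either, since 5.18 recalls antibody-positive subjects. Finally, applying the 24% placebo mortality would raise the upper end to 0.096 / 0.856 = 11.2%. Antibodies to ART-123 chiefly concern the ART-123 arm, although SAP 2.5 allows that some positives will not have taken the drug, so 4.5-7.1% is the relevant range.

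The reply does not remove the two groups with no stated route: earlier positives who die, and earlier positives who are negative by Day 28.

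**Conclusion.** The gap is real but minor. On the plan's wording, a neutralizing result is conditional on surviving and staying positive to Day 28 (or to an End of Study visit, which excludes deaths), and the protocol and SAP do not state the same rule for who is tested. The 4.5-7.1% rests on the plan's 16% mortality and on an assumed 60-75% of deaths before Day 14. It applies only to antibody-positive subjects, whose number the documents do not give and which may be very small. Nothing here touches the primary endpoint, the efficacy analyses or anti-drug antibody incidence.

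**What to change.** In Protocol 5.15 and 5.18, replace the Day 28 or End of Study condition with a statement that every confirmed-positive post-baseline sample (Day 14, hospital discharge, Day 28 or End of Study) is tested for neutralizing antibodies. Put the same rule in SAP 4.4.3, so that a missing neutralizing result has one meaning.

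The cost is wording in two protocol sections and one SAP section, and a few extra assays on serum already drawn. It needs no new visit or blood draw. The one practical limit is retained sample volume, which the documents do not describe. Neutralizing assays on matched baseline samples or a new reporting ratio would go beyond what this gap requires.
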